Power and Sample Size Justification: The sample size calculation and power analyses are based on the primary outcome of change in HRQOL between baseline and 12 months post intervention. The minimum sample size was based on detecting a clinically meaningful difference of 0.35 standard deviation units (medium effect) based on prior studies.[87,93,139-143] Essentially, this is equivalent to testing the interaction between time and group. Assuming 3 measurement time points, level of significance p=0.05, two-tailed comparison, correlation between pairs of measurements within participants (interclass correlation) no larger than p=0.6, compound symmetry covariance structure, we estimate that 123 participants per group (total n=246) are needed to detect, with 80% power, a standardized effect size of at least 0.35sd. This sample size includes a 20% inflation for attrition at 12 months. This effect size is robust enough to provide sufficient power for the outcomes listed under aims 1 and 2 and is consistent with data from our pilot study of 20 mentees and 7 mentors (see preliminary data). The pre-post differences in the outcomes (such as overall social support, positive social interaction, tangible support, vitality, emotional support, social functioning, general health, coping, etc), ranged from 0.35 to 0.88 standard deviation units. Although these calculations account for within patient clustering through the intera-class correlation mentioned above, clustering within mentors and mentees are assumed to have minimal intra-class correlation based on pilot data, especially since the cluster sizes would be at most 3 at a given wave. However, a multi-level model will be used in the analysis to verify this. Since the effect size planned is conservative, if the clustering leads to higher intra-class correlation, we would still be able to detect meaningful differences. We will also consider including mentor as a fixed effect in the model.

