
AIM 2: Determine the impact of a peer mentorship intervention in African American women with SLE on clinical indicators of disease activity and clinical profile that indicates success of the intervention. Analyses for Aim 2 will focus on estimation of efficacy as determined by: change in disease activity of ≥4 point reduction from baseline in SLEDAI score, in concordance with the accepted SLE Responder Index (SRI).[147] For comparative statistical assessments, the two groups will be compared using a generalized linear mixed models (GLMM) approach.[148] This approach allows for measurement of participants at different time points, missing data under the assumption of missing at random (MAR), and can also account for the effect of correlated longitudinal measurements within participants. In addition, GLMM accommodates a wide range of distributional assumptions such as dichotomous (e.g. binomial), count (e.g. Poisson), continuous (e.g. Gaussian), and categorical or ordinal outcomes. Additionally, outcomes that are measured longitudinally (at 6 and 12 months) will have intervention group, time, and time-by-intervention group as primary independent variables in the model. Additional adjustment covariables will be added to the model in a second set of analyses, when indicated. The magnitude of between intervention differences in outcome variables (effect sizes) at each time point will be estimated using appropriate contrasts in the corresponding GLMM models. We will then perform a responder analysis to develop a profile of the clinical and laboratory characteristics that predict success of the intervention. For this, a multivariate regression logistic regression model where the outcome is success (/failure) and the difference in the clinical (SLEDAI components) levels over time are independent variables. We will use model selection approaches such as the all subsets selection, to identify the important clinical and laboratory features in the presence of others. As much as the data allows, we will also consider interactions of the SLEDAI components. As an alternative to logistic regression, we will also consider other approaches such as the CART, or logic forest to efficiently identify the clinical and laboratory characteristics that predict intervention success.

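### The main Aim 2 responder model does not pre-specify baseline SLEDAI as a covariate, so a valid between-arm test is less sensitive than the data to be collected allow

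*Combined protocol and SAP*

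**What the plan says.** All references are to the combined protocol and SAP.

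- **Endpoint.** The AIM 2 paragraph of the Overview of Statistical Analysis Plan judges efficacy by "change in disease activity of ≥4 point reduction from baseline in SLEDAI score".
- **Main model.** Arms are compared by a generalized linear mixed model (GLMM), in which "outcomes that are measured longitudinally (at 6 and 12 months) will have intervention group, time, and time-by-intervention group as primary independent variables".
- **Adjustment.** "Additional adjustment covariables will be added to the model in a second set of analyses, when indicated". The covariables are not named. The closest stated rule is in the AIM 1 paragraph, which adjusts for covariates found to be unbalanced after randomisation.
- **Covariate list.** The list for all three aims covers demographics, BILD damage, coping, depression, anxiety, stress, health literacy, social support, trust and patient-centred care. It does not contain SLEDAI.
- **Entry.** Neither Study Eligibility criteria nor the fuller mentee criteria in the human-subjects section sets a SLEDAI minimum. Study Overview (B4b) speaks of women with active SLE but gives no threshold.
- **Power.** The Power and Sample Size Justification is "based on the primary outcome of change in HRQOL between baseline and 12 months post intervention". It then states that the effect size gives sufficient power for the Aim 1 and Aim 2 outcomes. It contains no responder calculation.

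**The concern.** The baseline score defines the Aim 2 outcome and then has no pre-specified place in the model that tests it. In the AIM 1 paragraph, by contrast, the worked example models baseline as one of the visits.

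With a fixed-point drop, the starting score decides who is able to respond at all and shapes the chance for everyone else. It is therefore likely to be the strongest predictor available. Leaving it out widens the uncertainty around the mentoring effect for Hypothesis 2.

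Leaving adjustment to a later, conditional analysis also means that Aim 2 may produce two results with no rule for which one counts.

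**Working it through.** **1. The plan's own figure.** Inputs from the Power and Sample Size Justification: "level of significance p=0.05, two-tailed comparison", 80% power, 0.35 SD, and correlation "no larger than p=0.6, compound symmetry covariance structure".

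- Two means: 2 × ((1.96 + 0.8416)/0.35)² = 128.1 per arm.
- Change score under compound symmetry: 128.1 × 2(1 − 0.6) = 102.5.
- 20% inflation: 102.5 × 1.20 = 123.0.

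This reproduces the stated 123 per group. The figure is for a continuous HRQOL change and says nothing direct about a SLEDAI responder outcome.

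**2. Who can respond.** SLEDAI cannot go below 0, so a 4-point fall needs a baseline of at least 4. This is arithmetic and needs no outside data.

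**3. How strongly baseline predicts response (illustration).** Assume a skewed score with mean 6 and SD 4, baseline to follow-up correlation 0.6, and no treatment effect. Simulated response rates are:

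| Baseline SLEDAI | Response |
|---|---|
| 0–3 | 0% |
| 4–5 | 2% |
| 6–7 | 13% |
| 8–11 | 31% |
| 12 or more | 58% |

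**4. Power with and without baseline.** Method: gamma scores rounded to integers; baseline and follow-up linked by a Gaussian copula; a 0.35 SD latent shift in the mentored arm; response is a fall of 4 or more; Wald test for arm in a logistic regression at one visit. The 0.35 SD and the 0.6 are borrowed from the HRQOL calculation, and 0.7 is the other correlation the plan gives (section B4c). The SLEDAI means and SDs, the 0.3 correlation and the entry floors are assumptions.

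| Mean, SD | Correlation | Entry floor | Per arm | Without | With | Gain (points) |
|---|---|---|---|---|---|---|
| 6, 4 | 0.6 | none | 123 | 31% | 43% | 12 |
| 6, 4 | 0.6 | none | 150 | 37% | 54% | 17 |
| 8, 5 | 0.6 | none | 123 | 38% | 49% | 11 |
| 8, 5 | 0.6 | none | 150 | 44% | 60% | 16 |
| 4, 4 | 0.6 | none | 123 | 21% | 34% | 13 |
| 6, 4 | 0.7 | none | 123 | 37% | 49% | 12 |
| 6, 4 | 0.3 | none | 123 | 22% | 34% | 12 |
| 6, 4 | 0.6 | 4 | 120 | 44% | 57% | 13 |
| 6, 4 | 0.6 | 6 | 120 | 64% | 68% | 4 |

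The no-floor rows used 1,500 runs each, so the Monte Carlo standard error of a power near 40% is √(0.4 × 0.6/1500) = 1.3 points. Differences of a point or two between rows mean little. With no treatment effect (mean 6, SD 4), type I error was 5.4% without and 5.0% with the covariate.

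**5. Wider assumptions.** A second approach fixed the response rates instead. Take 20% v 35%, 120 per arm, mean baseline 6, and about 61–69% of women able to respond. Unadjusted power is 73–76%. Adding linear baseline gives:

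- 77–80% if baseline matters only through the 4-point threshold;
- 80–85% with a log-odds slope of 0.1 per point;
- 88–91% with a slope of 0.25;
- 96–98% with a slope of 0.5.

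Over all such settings with no floor and 120 to 150 per arm, the gain ran from about 1 to 28 points.

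A joint score model with a 15-point difference in response and correlations of 0.3 to 0.7 gave gains of 16 to 25 points with no floor and 3 to 11 with a floor of 4 or 6. Its adjusted fit used only women able to respond, so its no-floor figures are not exactly the gain from the covariate alone.

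**6. Chance imbalance.** With 69% able to respond and 120 per arm, the SD of the between-arm difference in that share is √(2 × 0.69 × 0.31/120) = 6.0 percentage points. At an assumed 40% response among those women, one SD moves the responder difference by 0.40 × 6.0 = 2.4 points. The range over the settings tried was about 2 to 2.6. This variation is already in the unadjusted standard error.

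**The case against.** **The size cannot be derived from the plan.** This stands. The plan gives no SLEDAI mean, SD, correlation or response rate, and its 0.6 is an upper bound for HRQOL. The simulation is a single-visit regression, whereas the plan has a repeated-measures GLMM. The figures are illustrations; only the direction is firm.

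**The plan recruits women with active SLE.** If that were enforced as a minimum score, few or no women would be unable to respond and the gain would shrink, to about 4 points in the floor-of-6 row. This stands as a limit on size. No threshold is written, however, and the gain stayed positive in every floored case.

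**The plan allows adjusted analyses.** A reader might infer that baseline is shut out altogether. The text does not say so: it lists primary terms and then permits more. The fault is narrower. Baseline SLEDAI is not named, and adjustment is secondary and conditional. Prognostic strength known in advance is a better ground for adjusting than imbalance seen afterwards.

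**Chance imbalance is ordinary sampling variation.** A reader might infer that the unadjusted comparison is biased if one arm happens to start higher. Under randomisation it is not, and unadjusted type I error stayed at about 4 to 6%.

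**Baseline SLEDAI may not exist for everyone.** Recruitment of Mentees lets women outside MUSC take part without travelling, while the Aim 2 methods take SLEDAI from the MUSC database or a visit there. The Data Collection Schedule makes month 6 questionnaire only, although the Aim 2 model uses month 6. Both conflicts are real and limit where the covariate can be applied.

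**Conclusion.** The point holds as one of efficiency. The main Aim 2 model omits a baseline value that the plan already intends to collect and that determines who can respond. The unspecified second analysis does not make good the omission.

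The unadjusted test is valid. Under the assumptions shown, naming baseline SLEDAI would raise power by:

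- about 11 to 17 points with no entry floor under the skewed-score model;
- about 3 to 13 points if all entrants start at 4 or 6 or more;
- about 1 to 28 points over everything tried.

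No single figure should be quoted as the loss.

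A reader might also infer that the covariate would make good the plan's statement that power is sufficient for Aim 2. It would not. In the table above, adjusted power is 34 to 60% with no floor and at most 68% with one, all below 80%. That statement rests on a calculation for a continuous HRQOL outcome and needs its own responder calculation whichever model is used.

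The change is worth making before the data are analysed. It does not bear on the validity of the trial.

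**What to change.** In the AIM 2 paragraph of the Overview of Statistical Analysis Plan:

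1. Name each woman's continuous, pre-randomisation SLEDAI as a fixed covariate in the main GLMM, at each visit where SLEDAI is obtained, and state that this is the analysis that counts.
2. Report the arm difference as a risk difference standardised over the observed baseline distribution, beside the odds ratio.
3. Keep the unadjusted responder proportions as a descriptive table.
4. Say how women who start below 4 are counted.
5. Treat baseline SLAQ in the same way for any SLAQ outcome.

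Do not describe the covariate as correcting a bias or as securing the Aim 2 power. The statements on remote participation and on the month 6 assessment need reconciling with the Aim 2 model, so that it is clear at which visits, and for whom, SLEDAI will exist.

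**Cost.** A few lines of text, with no new data or visits. The one small downside is that the adjusted odds ratio is conditional on baseline, which is why the standardised risk difference should stand beside it.

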Disease activity will be assessed using both physician assessment and patient-reported outcome measure. The Systemic Lupus Activity Questionnaire (SLAQ)[131] asks a single Patient Global Assessment (PGA) question about presence and severity of lupus activity over the past month, questions on 24 specific symptoms of disease activity and a single Numerical Rating Scale (NRS) asking the patient to rate disease activity on a scale of 0-10 over the past three months. Use of immunomodulatory drugs and prednisone (total dose and tapers) will also be assessed. For physician assessment of disease activity, the Systemic Lupus Erythematosus Disease Activity Index (SLEDAI) has been individually validated and found reliable in clinical trials. SLEDAI scores are routinely collected as part of regular visits and clinical, demographic, genetic, disease activity/damage, genetic, and laboratory data are stored in the longitudinal web-based SLE database at MUSC as part of NIH-funded P60 and P30 grants (see [name] biosketch). All clinicians recording SLEDAI scores are trained in this assessment with annual refresher courses as part of their participation in industry-sponsored clinical trials. SLEDAI scores for each participant will be extracted from the database when available for dates within the same month as baseline, mid-intervention, and post-intervention data collection points. When scores are not available in the database, the participant will be scheduled for a clinic visit that will include vitals, blood collection, and labs to ascertain SLEDAI score. Clinic visits will take place within the South Carolina Clinical & Translational Research Institute (SCTR) Research Center (Research Nexus) at MUSC. The SC will coordinate questionnaire administration, clinic visits for SLEDAI ascertainment, and data entry. Physical examination and laboratory evaluation will be achieved by in-person clinic visit when recent SLEDAI scores are not available in the database record of a given participant. Social support control participants and mentors will complete assessments on the same schedule as mentored participants. The SLEDAI is a multicomponent, 24 question survey of clinical and laboratory signs and symptosm used as a representation of a physician's assessment of a patient's disease activity over the last 30 days (see Appendix). Items are weighted based on their severity ranging from a multiplier of 8 to no multiplier (i.e. 1). The maximum 'score' for the test is 105.[132] Validated clinically meaningful changes in SLEDAI scores are -6 for improvements and +8 for worsening disease activity.[133]

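### Aim 2's responder profile is built from post-baseline changes in SLEDAI components with no arm term, so it cannot show who benefits from mentoring

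*Combined protocol and SAP*

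**What the plan says.** All references are to the combined protocol and SAP.

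- **Efficacy criterion** (Overview of Statistical Analysis Plan, AIM 2): the analyses "will focus on estimation of efficacy as determined by: change in disease activity of ≥4 point reduction from baseline in SLEDAI score".
- **Between-arm comparison** (same paragraph): a generalized linear mixed model (GLMM), for which "outcomes that are measured longitudinally (at 6 and 12 months) will have intervention group, time, and time-by-intervention group as primary independent variables".
- **Profile** (same paragraph): a responder analysis is then meant to "develop a profile of the clinical and laboratory characteristics that predict success of the intervention". It is a logistic model in which "the outcome is success (/failure) and the difference in the clinical (SLEDAI components) levels over time are independent variables". All-subsets selection is proposed, with CART or logic forest as alternatives. On interactions the text says only that "we will also consider interactions of the SLEDAI components". It names no arm term, no baseline values, no interval for the changes and no analysed population.
- **Score** (Methods for AIM 2): "The SLEDAI is a multicomponent, 24 question survey of clinical and laboratory signs" and symptoms. Items carry weights from 1 to 8 and the maximum is 105. This section also cites a change of -6 as a meaningful improvement. Hypothesis 2 names the patient-reported SLAQ beside SLEDAI.
- **Effect modification elsewhere:** stratified analyses by age and comorbidity count (B4d), and depression, trust and social support as moderators (exploratory aim). Neither covers clinical or laboratory features.

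**The concern.** A profile that predicts success of an intervention should say, from what is known when mentoring is offered, which women gain more from mentoring than from the support group. The specified model differs from that in two ways. Its predictors are observed only after mentoring has begun, and on the natural reading they are the parts of the outcome itself. It also has nothing that compares the arms, so an item linked to improvement in everyone looks the same as an item that marks benefit from mentoring.

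The clinical profile is the second half of a numbered aim, and no other section plans an analysis that would supply it. A published profile could be read as guidance on whom to offer mentoring, although much the same items would be selected if mentoring had no effect.

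**Working it through.** **1. Algebra of the outcome.** Let x_j be item j and w_j its weight (24 items, Methods for AIM 2). The score is S = Σ w_j x_j. With d_j the fall in item j between two visits, the fall in score is Σ w_j d_j, so on the 4-point reading

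success = 1 if Σ w_j d_j ≥ 4, otherwise 0.

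In a logistic model on all 24 changes, put β_j = c·w_j and intercept -3.5c (whole-number scores). As c grows, every fitted probability goes to 0 or 1. Separation is complete and there is no finite maximum-likelihood estimate. This needs no assumption about item frequencies. With the -6 threshold the algebra is the same, with 6 for 4. Only a different interval or an outcome not based on SLEDAI breaks the identity.

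**2. What the profile would have to estimate.** For a baseline feature Z, arm A and success Y:

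[P(Y|A=1,Z=1) - P(Y|A=0,Z=1)] - [P(Y|A=1,Z=0) - P(Y|A=0,Z=0)].

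The planned model estimates P(Y | changes), with neither A nor baseline Z. A mentored-only fit gives two of the four terms, so it cannot form the contrast either.

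**3. Size, by simulation.** The documents give no item frequencies or responder rates, so these inputs are assumptions: 240 completers; weights 8×8, 6×4, 7×2 and 3×1 (64 + 24 + 14 + 3 = 105, the stated maximum); item prevalences 2-30%; success = fall of at least 4 at month 12.

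| Check | Result |
|---|---|
| Full 24-change model, same interval | separated in 108 of 108 sets |
| Month-6 changes predicting month-12 response | separated in 0 of 108 |
| 5- to 12-item subsets, no mentoring effect, same interval | cross-validated AUC 0.70-0.90 |
| Same subsets, month-6 changes, no mentoring effect | AUC 0.55-0.73 |
| Same subsets, uniform mentoring effect | AUC 0.70-0.90 (same interval), 0.58-0.74 (month-6 changes) |
| Common 4-point item in 8-item profile, no effect | selected in 98% |
| 2-point item, mentoring helps only women with it | selected in 60% |
| 2-point item, prognostic in both arms, mentoring does nothing | selected in 57% |

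Good discrimination and a plausible item list therefore appear with or without a mentoring effect.

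**4. What a corrected analysis can and cannot do.** An arm-by-baseline test of that 2-point item rejected in 46% of sets when mentoring helped only women with it, and in 5% when it was merely prognostic. That is one item known in advance and is not comparable with a search. Across null sets, testing arm interactions item by item gave at least one p<0.05 in 42-63% over two separate runs. A joint model with all baseline items and their arm interactions was completely or quasi-separated in 70-100%.

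Precision for one pre-specified binary predictor, with 150 × 0.8 = 120 completers per arm, response p = 0.3 (assumed) and predictor frequency f:

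SE = √[2p(1-p)/(120f) + 2p(1-p)/(120(1-f))].

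- f = 0.5: √(0.42/60 + 0.42/60) = 0.118; 95% CI ±23 points; 80% power at 2.802 × 0.118 = 33 points.
- f = 0.2: √(0.42/24 + 0.42/96) = 0.148; 95% CI ±29 points; 80% power at 41 points.

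**5. Separate minor point: power.** Power and Sample Size Justification sizes the trial on continuous HRQOL: 2(1.960 + 0.842)² × 2(1 - 0.6)/0.35² = 102.5; × 1.2 = 123.0 per group, which matches the plan. It then claims sufficient power for Aims 1 and 2, with no responder rate and no binary calculation. At 120 per arm and assumed control rates of 10-50%, 80% power needs a responder difference of 13-18 points. If a 0.35 SD shift is dichotomised (normality assumed), power is 40-58%, against 77% for the continuous outcome. At 0.35/√0.8 = 0.391 SD of change it is 48-67%, against 86%.

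**The case against.** The strongest reply is that the text is ambiguous, not wrong. Success is undefined, the section on Aim 2 methods cites -6 as well, and a SLAQ-based success would remove the exact circularity. The aim's title speaks of a profile that indicates success, and component changes suit a description of what improved in responders. Complete separation belongs to the full 24-change model, whereas the plan proposes subset selection, CART or logic forest. The simulated percentages rest on assumed inputs.

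Much of this stands. A reader might infer that the profile model can never be fitted; the documents do not support that, since subset, tree and lagged versions avoid separation. The simulated figures illustrate and do not measure. What does not stand is the rescue of the stated purpose. The analysis sentence says predict, not describe. Under every definition the predictors are post-baseline and no arm contrast is listed, and the tree methods are offered with no other predictors and no arm term. Nor is the profile labelled exploratory.

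A further fair objection is that replacing component changes with all 24 baseline items and their arm interactions would bring back separation and false positives (step 4). The fix must therefore be restricted.

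**Conclusion.** Wrong as written, limited to the Aim 2 responder profile, and worth fixing before analysis. Post-baseline component changes without an arm-by-predictor contrast cannot identify who benefits from mentoring. That conclusion follows from the text and needs no simulation. Exact circularity is conditional: success must be a SLEDAI reduction measured over the same interval as the component changes.

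Two stronger readings are not supported. A reader might infer that the Aim 2 efficacy comparison is compromised; it is not, because the GLMM contains arm, time and their interaction. A reader might also infer that the responder endpoint is underpowered. The documents give no responder rate, the power figures above assume rates, normality and a single-visit test, and the planned GLMM uses 6 and 12 months. All that is established is that power for the binary response is asserted and not shown.

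**What to change.** In the SAP text for Aim 2:

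1. State the success criterion, time point and analysed population for the profile, and reconcile the 4-point criterion with the -6 cited in the methods.
2. Replace component changes with baseline clinical and laboratory values.
3. Fit both arms together with arm and arm-by-predictor terms, either for a short pre-specified list (for example baseline total SLEDAI and a few grouped organ domains) or in a penalised model. Do not enter all 24 items with interactions. State the internal validation and the handling of multiplicity.
4. Adjust for baseline total SLEDAI and report how many women start below 4 points. They cannot achieve a 4-point reduction, and neither eligibility list sets a minimum score.
5. Label the profile exploratory, report interactions with 95% CIs, and show component changes only as a descriptive table by arm.

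Separately, in Power and Sample Size Justification, restrict the power statement to continuous outcomes or add a binary calculation with a stated control rate. The responder endpoint can stay.

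The cost is SAP wording, provided item-level baseline SLEDAI is available. That must be confirmed: the methods promise that "SLEDAI scores for each participant will be extracted from the database when available", which speaks of scores and not items, and Recruitment of Mentees lets women outside the centre take part without travelling there. The downside is imprecision: only large differences in benefit between subgroups (33 to 41 points for 80% power under the stated assumptions) could be detected reliably.

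### The Aim 2 success profile is selected and judged on the same data, from changes in the items that make up the SLEDAI, with no shrinkage or validation stated

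*Combined protocol and SAP*

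**What the plan says.** The AIM 2 paragraph of the Overview of Statistical Analysis Plan follows the group comparison with a responder analysis. This is a logistic model in which "the outcome is success (/failure) and the difference in the clinical (SLEDAI components) levels over time are independent variables". Features are chosen by a search, using "model selection approaches such as the all subsets selection, to identify the important clinical and laboratory features". The search may widen: "As much as the data allows, we will also consider interactions of the SLEDAI components". As an alternative, "we will also consider other approaches such as the CART, or logic forest".

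The only responder criterion in that paragraph is a "change in disease activity of ≥4 point reduction from baseline in SLEDAI score". The plan ties it to the SLE Responder Index but does not define success separately for the profile model.

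The candidate set comes from Methods for AIM 2: "The SLEDAI is a multicomponent, 24 question survey of clinical and laboratory signs". Items carry multipliers from 1 to 8, and the maximum score is 105.

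No selection criterion, penalty, hold-out sample, cross-validation or bootstrap is given for this step. The Tukey-Kramer adjustment belongs to the Aim 1 secondary time points, and the bootstrap belongs to the Aim 3 cost models.

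**The concern.** Two features of this step combine. First, features are selected and then judged on the same women, with many candidates and few events, which makes apparent accuracy optimistic. Second, if success is the SLEDAI fall, the predictors are the pieces from which the outcome is computed. The model would then largely restate the score. Item changes are also known only after follow-up, so they cannot show in advance who will benefit.

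The profile is named in the wording of Aim 2. The plan labels some other analyses exploratory, but not this one. A reader could therefore take the selected features, and any accuracy quoted for them, as an Aim 2 result that would hold in other women.

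**Working it through.** **The plan's own figure.** The profile has none. The trial's sample size, set for HRQOL, reproduces as a change score under compound symmetry: 2(1.960 + 0.842)² × 2(1 − 0.6)/0.35² = 102.52 per group, and × 1.2 = 123.02, the stated 123. It says nothing about the profile.

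**Women available.** Planned enrolment is 300 (150 per arm). With 20% attrition, 300 × 0.8 = 240 in both arms, or 150 × 0.8 = 120 in the mentored arm. The plan does not say which set is used.

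**Candidates.** There are 24 main effects and 24 × 23/2 = 276 pairwise interactions, 300 in all.

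**Events per candidate.** The documents give no responder rate, so 20% to 40% is assumed.
- 240 women: 48 to 96 events, or 2 to 4 per main effect. With all pairs this is 48/300 = 0.16 to 96/300 = 0.32.
- 120 women: 24 to 48 events, or 1 to 2 per main effect.

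**Reading A: success is the SLEDAI fall of at least 4.** Let d_j be the change in item j and w_j its weight. Success occurs exactly when Σ w_j d_j ≤ −4. A logistic model with all 24 changes can reproduce this rule through coefficients proportional to −w_j, so it separates the groups completely and finite maximum-likelihood estimates do not exist.

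The simulation assumed:
- weights of 8 for eight items, 4 for six, 2 for seven and 1 for three (64 + 24 + 14 + 3 = 105);
- item prevalences of 3% to 30%, with items independent;
- about 26% responders as a result, and 4,000 new women for testing.

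| Women | Model | Items kept | Apparent AUC | New-data AUC |
|---|---|---|---|---|
| 240 | all items | 24 | 1.00 | 0.98 |
| 240 | after BIC search | about 20 | 1.00 | 0.95 |
| 120 | all items | 24 | 1.00 | 0.94 |
| 120 | after BIC search | 15 | 1.00 | 0.89 |

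The all-items rows use 200 simulated trials each, and every one separated completely. The BIC rows use 15 each. A separate run gave new-data AUC of 0.97 at 240 and 0.91 to 0.92 at 120, inside these ranges.

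**Reading B: success is something unrelated to the items.** A null candidate is kept with probability P(χ²₁ > penalty).
- AIC, penalty 2: 0.1573, and 24 × 0.1573 = 3.8 false features.
- BIC, penalty ln 240 = 5.48: 0.0192, and 24 × 0.0192 = 0.46.

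Simulation with 30% responders and a backward search standing in for all-subsets:

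| Women | Criterion | False features kept | Apparent AUC (true 0.50) |
|---|---|---|---|
| 240 | AIC | 4.3 | 0.65 |
| 240 | BIC | 0.56 | 0.55 |
| 120 | AIC | 5.6 | 0.73 |
| 120 | BIC | 0.98 | 0.59 |

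Separate runs at 240 gave 4.35 (apparent AUC 0.64) and about 5 features for AIC, and 0.3 features for BIC, where the low end of apparent AUC is 0.52.

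**The case against.** A reader might infer that the profile will be made up of chance features. The documents do not support that. It requires items unrelated to success, whereas the only stated responder criterion is built from those items, so under Reading A the selected items are mechanically related to the outcome. Even under Reading B, the count falls from about 4 to 5 with AIC to about 0.3 to 0.6 with BIC, and the plan names neither. All-subsets is given only as an example, and interactions are limited by what the data allow. Nor does the number of possible subsets (2²⁴, about 16.8 million) measure the problem: the false-feature count follows from the penalty and the number of candidates.

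A reader might also infer that penalisation alone cures this and shortens the profile. It does not. On the Reading A design with 240 women and 37% to 45% responders, a cross-validated lasso kept about 22 of 24 items, with AUC 1.00 apparent and 0.99 in new data. Validation would then endorse a model that restates the score.

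Finally, Hypothesis 2 concerns only group differences in SLAQ and SLEDAI. No power claim or decision rests on the profile, and the plan does not commit to reporting an AUC.

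All of this stands, and it limits the point. It does not supply the missing success definition, selection rule or validation. It also does not remove the optimism, which appears under both readings, or the separation under Reading A.

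**Conclusion.** The point holds in limited form. As written, the step gives no protection against over-favourable accuracy, and how far accuracy is overstated cannot be fixed until success and the selection criterion are stated.

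- **Success is the SLEDAI fall:** the AUC gap is modest, roughly 0.02 to 0.05 at 240 women and 0.06 to 0.11 at 120 (1.00 less the new-data values). The larger defects are unusable unpenalised estimates and a profile that restates the score.
- **Success is unrelated to the items:** at 240 women the apparent AUC exceeds the true 0.50 by about 0.15 with AIC or 0.02 to 0.05 with BIC.

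The complete separation of the all-items model under Reading A is algebraic. The other sizes rest on assumed responder rates, item prevalences, weights and independence, none of which the documents give. Importance is minor: the profile is a follow-on analysis, and the between-arm efficacy comparison does not depend on it.

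**What to change.** Amend the AIM 2 text to:
1. define success for the profile model and say which arm or arms enter it;
2. take predictors from a pre-listed set of baseline characteristics, not from changes in the items that make up the score;
3. fit a penalised logistic model (lasso or elastic net) and state how the penalty is chosen;
4. report bootstrap optimism-corrected AUC and selection frequencies, repeating the whole selection step in each resample, and do the same for CART or logic forest;
5. label the profile exploratory.

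Items 1 and 2 are essential, because items 3 and 4 alone leave the overlap between outcome and predictors in place. Baseline predictors keep a weaker mechanical link, since a woman scoring below 4 at baseline cannot fall by 4. Baseline total SLEDAI should therefore be on the list and the link acknowledged.

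The cost is SAP wording, modest computing and less impressive reported accuracy. No change to data collection, sample size or the efficacy analysis is needed.
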